## **8.9. Wearable Devices**

The Apple Watch Series 6 will be worn snugly on the left or right wrist according to patient's preference. The participants will rest their arm comfortably on their lap. The investigator will open the ECG app on the Apple Watch. With the hand opposite to the watch the participant will be asked to hold their finger on the digital crown to generate a 30-second 1-lead ECG. During the same 30 seconds a simultaneous 12-lead ECG recording will be performed. The Apple Watch recording will be stored in the research iPhone SE Health app (with no identifiable data), uploaded to the iCloud and will be exported in PDF format for analysis.

The SkyLabs CART-I ring will be worn on the same hand as the Apple Watch, preferably in the ring finger. Similarly, a simultaneous 30-seconds recording with a 12-lead ECG will be performed with the participant resting his/her hand comfortably. A 30-second 1-lead ECG can be generated by placing a finger from the opposite hand on the metal casing and selecting the 'measure' tab in the CART-I ring app. The SkyLabs recording will be stored in the CART-I Ring app and uploaded to the SkyLabs CRM account (with no identifiable participant's data) and will be exported at a later date in PDF format for analysis.

If the first recording of any of the wearable devices has artefacts a second recording will be allowed, and the first recording discarded. The order of the devices will be randomly selected at the time of the baseline visit.

By enrolling in the study, participants will likely extend their hospital visit by 20-30 minutes to complete all study procedures. A minimum of 10 minutes will elapse before the device is used by a different participant.

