The purpose of this study is to test how well two commonly used innovative wearable devices — the SkyLabs CART-I ring and the Apple Watch — detect different cardiac arrhythmias. We plan to recruit 500 patients attending Cardiology Departments in several hospitals in the UK and will have a 12-lead ECG as part of their care. Participants will first have a simultaneous 12-lead ECG with a 1-lead ECG from one of the two wearable devices. This will be followed by a second (extra) 12-lead ECG with a 1-lead ECG from the remaining wearable device. Therefore, in addition to their usual 12-lead ECG, participants will have one extra 12-lead ECG and two extra 1-lead ECGs. No extra follow-up visits are required. At the end of the study, we will compare interpretation by heart rhythm specialists of the 1-lead ECGs recorded by the wearable devices and the 12-lead ECG.

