By placing a finger in the metal portion of the ring, a high quality 30-second single-lead ECG and PPG signal is created in its smartphone app. The automatic analysis will classify the recording as sinus rhythm, atrial fibrillation or uninterpretable.

Rationale: Wearable technologies have the potential to improve the management of patients with atrial fibrillation and other cardiac arrhythmias. Their utility is dependent on having an accurate, reproducible 1-Lead ECG and very sensitive (and reasonably specific) detection of cardiac arrhythmias, including atrial fibrillation. This observational study will investigate the accuracy of two contrasting wearable devices: the Apple Watch Series 6 and the SkyLabs CART-I ring.

**Figure 1.** SkyLabs CART-I ring and Apple Watch Series 6

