## 7. STUDY DESIGN

This study is a prospective, multicentre, observational study comparing rhythm and heart rate detection of two novel wearable devices — the Skylab CART-I ring and Apple Watch Series 6 — to a 12-lead ECG (gold-standard) for different cardiac rhythm disorders. We will recruit 500 participants attending Cardiology outpatient appointments, procedures or investigations (including the catheterisation laboratory) and inpatients in the cardiology and cardiothoracic wards in three hospitals across the UK. All patients will be due a 12-lead ECG as part of their standard of care.

If participants agree to take part in this study, the research team will provide them with instructions and will demonstrate how to use the wearable devices. Participants will then be asked to perform a simultaneous 30-seconds 12-lead ECG and 1-lead ECG for each wearable device (Skylab CART-I ring or Apple Watch). The order of recordings will be randomly assigned. If the first recording is uninterpretable due to artefact, a second recording will be allowed.

[figure not shown]
The SkyLabs CART-I Ring generates a 30-second 1-lead ECG by placing the participants finger on the rings' metal casing. Similarly, the Apple Watch 1-lead ECG requires the participant to place his/her finger on the metal crown. The 1-lead ECGs will be displayed and saved in the CART-I ring app and Apple Health app of a research iPhone SE, respectively. The smartphone apps will not contain any identifiable data and participants will only be identified by the time stamp of their recordings. The clocks of the Apple Watch, SkyLabs CART-I ring and ECG machine will be synchronised. The 12-lead ECG will also contain a time stamp and the study ID number (site code and participant number), it will then be recorded by using the iPhone SE camera and exported in PDF format for subsequent analysis. The 12-lead ECGs time stamp will also be documented in the CRF. The 12-lead ECGs will be added to the participants medical notes and available to the clinical team. The 1-lead ECGs from the wearable devices will only be available to the research team.

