This study does not involve any follow-up visits. All the 1-lead ECGs stored in the CART-I Ring app and Apple Health app will be exported in PDF format. All ECGs (12-lead ECGs and 1-lead ECGs from the wearable devices) will be analysed by two Cardiologists (based at Oxford University Hospital NHS Foundation Trust/OUHFT) blinded to patient's data. Any disagreement will be resolved by a third Cardiologist (CI of the study).

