## **8.7 Blinding**

Investigators and subjects will not be blinded to investigation arms during data collection. At the end of the follow-up, all the anonymised ECGs (12-lead and 1-lead from wearables), from all sites, will be adjudicated by two cardiologists blinded to patients' data.

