## 10 STATISTICS AND ANALYSIS

Descriptive statistics are reported as count and percentage for categorical variables and mean and standard deviation for continuous variables.

Adjudication of all anonymised ECGs (12-lead ECGs, 1-lead ECGs from Apple Watch and SkyLabs CART-I ring) will be performed by two Cardiologists blinded to participants' data. Any disagreements will be decided by a third Cardiologist (CI of the study). Following adjudication, the sensitivity, specificity, positive negative predictive values will be calculated for different cardiac rhythm disorders. The level agreement between adjudicators will be calculated using the Cohen's kappa.

ECG waveform analysis and intervals (PR, QRS, QT and RR) will be measured by using callipers to the nearest 0.25 mm. The first three consecutive waveforms will be analysed in each ECG and the intervals averaged. In the 12-lead ECG, it will be to the physician's discretion which lead is chosen to measure the

intervals. To investigate the level of agreement, correlation coefficient and Band-Altman plots will be generated.

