### **11.3 Data Recording and Record Keeping**

The participants will be identified by a unique study specific ID number (includes the site ID code and participant number) which will be assigned following consent. The study ID number (will be used in both hard-copies and electronic documents (PDF of 12-lead ECGs, excel spreadsheets for analysis and adjudication). The hard copies (CRF and consent forms) of data will be securely kept in the Research Fellows' Office at each site. The key to the study ID number for each site will be maintained on a single document will be kept in a separate folder in the PI's office.

The participants name and any other identifying detail will NOT be included in any trial data electronic file (PDF of 12-lead ECGs, 1-lead ECGs, excel spreadsheets for adjudication and analysis).

Each individual site will have an Apple Watch and SkyLabs CART-I rings (five different sizes) which will be paired with a research iPhone SE. No identifiable data will be recorded in the iPhone SE. Apple Watch 1-lead ECGs are transmitted to the research iPhone health app with no patient identifiable information. The time stamp on each ECG will be documented on the CRF and used to identify study participants. All the data pertaining to the Apple Watch will be stored in the research iPhone SE and uploaded to the iCloud so that it can be assessed remotely for adjudication. All 3 research iPhones (one per site) will be registered to a research account ([[contact]](mailto:[contact])) and thus all uploads to the iCloud can be accessed centrally by the investigators in OUHFT. Individual upload can be identified by the serial number for the CART-I rings and by the name of the Apple Watch (different for each site) and thus if there are two recordings with the same time stamp we can easily identify the site and match it to the matching 12-lead ECG.

The SkyLabs CART-I ring data is recorded to its app (CART-I smpl) in the iPhone SE and to a password protected Oxford CRM Skylab online account (<https://www.CART-Icardiotracker.com>; see Appendix C) created for the purpose of this study ([[contact]](mailto:[contact])). Only the investigators will have access to the

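### Wearable recordings with artefact may be repeated and the first discarded, under two different triggers and with no log, so accuracy describes up to two attempts and first-attempt failure goes unreported

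*Combined protocol and SAP*

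**What the plan says.** Two sections give the retake rule, and they differ.

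- Section 8.9 (Wearable Devices): "If the first recording of any of the wearable devices has artefacts a second recording will be allowed, and the first recording discarded". Any artefact is enough, and the first trace is dropped.
- Section 7 (Study Design): "If the first recording is uninterpretable due to artefact, a second recording will be allowed". The trace must be unreadable, and the fate of the first recording is not mentioned.

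Other sections bear on what happens next.

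- Section 8.7: "Investigators and subjects will not be blinded to investigation arms during data collection". No section says who decides on a retake or by what criterion.
- Section 10: "Following adjudication, the sensitivity, specificity, positive negative predictive values will be calculated for different cardiac rhythm disorders". There is no rule for uninterpretable, repeated or discarded recordings.
- Section 6 lists no failure-rate or first-attempt outcome.
- Section 7 also says: "All the 1-lead ECGs stored in the CART-I Ring app and Apple Health app will be exported in PDF format". Section 11.3 adds: "The time stamp on each ECG will be documented on the CRF and used to identify study participants". Neither says that a discarded first attempt is kept or counted, and no attempt number or retake reason is described.

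**The concern.** Failure to produce a readable trace is part of how a user-operated ECG device performs. Section 7.3 says the study should show the limitations of arrhythmia detection by these devices, and the discard rule removes some of the evidence on exactly that.

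Three things are at stake.

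- **What the accuracy figures mean.** They describe a first attempt where it is accepted and a second attempt otherwise. A reader could take them as the accuracy of a single recording.
- **Comparison of ring and watch.** With no definition and no log, retakes may be used more freely for one device, and nobody could tell afterwards.
- **The algorithm objective.** Section 5 says of the ring: "The automatic analysis will classify the recording as sinus rhythm, atrial fibrillation or uninterpretable". How often a first recording ends in that class is a result in its own right, and it is lost if such recordings are among those discarded.

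Adjudication by blinded cardiologists does not help, because they cannot assess a trace they never receive.

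**Working it through.** The documents state no artefact rate, retake rate or failure rate, so there is no figure of the plan's own to reproduce. The rates below are assumptions chosen to show scale.

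**Set-up.** Let q be the probability that a first trace has artefact, r the probability that the retake also does, S the sensitivity on clean traces and A the sensitivity on artefact traces. Assume every artefact trace is retaken.

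- First attempt: (1−q)S + qA
- Up to two attempts: (1−q)S + q[(1−r)S + rA]
- Difference: q(1−r)(S−A)

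**Independent attempts (r = q), S = 0.95.** A = 0.70 suits the wider trigger in Section 8.9, where a trace with artefact may still be readable. A = 0 (counted as a miss) suits the narrower trigger in Section 7.

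| q | A = 0.70: first → up to two | Difference | A = 0: first → up to two | Difference |
|---|---|---|---|---|
| 10% | 92.5% → 94.75% | 2.25 | 85.5% → 94.05% | 8.55 |
| 15% | 91.25% → 94.44% | 3.19 | 80.75% → 92.86% | 12.11 |
| 20% | 90.0% → 94.0% | 4.0 | 76.0% → 91.2% | 15.2 |

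**Correlated attempts.** If half of retakes also fail (r = 0.5), the difference at q = 10% is 0.10 × 0.5 × 0.25 = 1.25 points, or 0.10 × 0.5 × 0.95 = 4.75 points with misses. At q = 20% it is 2.5 and 9.5 points.

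**Check with a cited figure.** Section 5 cites 96% sensitivity for AF from a 50-patient watch study. With first-attempt failure rate f and failures counted as missed, sensitivity is 0.96(1−f) at first attempt and 0.96(1−fr) with up to two. The range runs from r = 0.5 to r = f.

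| f | First attempt | Up to two attempts |
|---|---|---|
| 5% | 91.2% | 93.6-95.8% |
| 10% | 86.4% | 91.2-95.0% |
| 20% | 76.8% | 86.4-92.2% |

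If failures are excluded from the table, sensitivity is 96% in every cell and the difference is zero. The counting rule, which Section 10 does not give, therefore matters as much as the artefact rate.

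**Effect on the device comparison.** Suppose one device had 10% artefact and the other 20%, with A = 0.70 and independent attempts. The gap between them is 92.5 − 90.0 = 2.5 points at first attempt and 94.75 − 94.0 = 0.75 points with up to two.

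**Can the first-attempt rate be inferred later?** The failure rate left after retakes is fr. A residual 2% fits f = 2% (r = 1), f = 4% (r = 0.5) or f = √0.02 = 14% (independent attempts). It does not identify f.

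**What a log would give.** With 500 first attempts per device, Wilson 95% intervals are 3.4% to 7.3% for 25/500, 7.7% to 12.9% for 50/500, and 16.7% to 23.7% for 100/500.

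**The case against.** Allowing a retake is reasonable for a device the user can simply operate again, and up to two attempts is a legitimate target if it is labelled as such. The primary objective does not specify the first attempt. That stands, and the point is not that retakes should be forbidden.

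Several stronger readings are tempting, and the documents do not support them.

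- **That the plan picks the better of two traces.** It does not. It keeps an accepted first trace, and otherwise the second, whatever its quality.
- **That all accuracy measures are biased upwards.** This holds only relative to first-attempt accuracy, and only under some counting rules. With failures excluded, the difference can be zero.
- **That the failure rate is irrecoverable.** Failures after the retake can still be counted. If discarding means only omission from analysis, stored files and time stamps might allow a partial count of first attempts. The plan does not provide for one.
- **That a retaken trace has no simultaneous reference.** Section 2 says "participants will have one extra 12-lead ECG and two extra 1-lead ECGs", but that sentence also counts only two 1-lead recordings, so it describes the case without a repeat. Section 7 defines each recording as simultaneous with a 12-lead ECG, and a retake may well follow the same procedure. The text is unclear; it does not show that the reference is missing.
- **That unblinded staff favour one device.** The arms are device orders, staff cannot be blinded to a ring or a watch, and no section says who decides. Differential retaking is possible but not shown.

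**Conclusion.** The point holds in limited form. Sections 7 and 8.9 set different retake triggers, Section 8.9 discards the first trace, and no other section provides a log, a failure-rate outcome or a counting rule. Followed as written, the plan yields accuracy for up to two attempts and makes no provision to report first-attempt failure.

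Accuracy may look better than at first attempt by about 2 to 4 points, or about 9 to 15 points if artefact counts as a miss. Both ranges assume 95% sensitivity on clean traces, 10-20% artefact, independent attempts and a retake whenever artefact occurs; the first also assumes 70% sensitivity on artefact traces. Correlated attempts shrink the difference, and excluding failures can remove it. None of these rates comes from the documents, so the direction is plausible and the size unknown.

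This is a cheap improvement, best made before recruitment because a deleted trace cannot be restored at analysis.

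**What to change.** - In Section 8.9, delete the clause that discards the first recording.
- Use one defined retake trigger in Sections 7 and 8.9.
- Retain every recording, and log attempt number, device and reason on the CRF.
- State that each retake is paired with its own simultaneous 12-lead ECG, and that the ECG count in Section 2 applies when no retake is needed.
- In Section 10, state how uninterpretable traces enter the 2×2 tables.
- Report first-attempt and up-to-two-attempt accuracy side by side, with first-attempt and final failure rates by device. Which of the two leads is a choice of estimand for the investigators; it should be declared in advance.

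The cost is protocol wording, a CRF field, some extra tracings to read and possibly a less favourable accuracy figure.

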## **8.8 Subsequent Visits**

This study does not include any planned subsequent visits or collection of follow-up data. Both 12-lead ECGs will be added to the clinical notes and available to the clinical team at the time of their appointment. However, if we pick-up any abnormal rhythms which were not previously known and not detected by the clinical team at the time of their appointment, we will inform the participants' clinical team and their GP. They will then decide if any action and/or follow-up is needed.

## **8.10 Early Discontinuation/Withdrawal of Participants**

This study only involves recording a 1-lead ECG from two wearable devices and does not include any follow-up visits. During the course of the study, which is anticipated to be only 20 minutes, a participant may choose to withdraw early from the study at any time. This may happen for a number of reasons, including but not limited to:

- The occurrence of what the participant perceives as an intolerable AE (severe skin reaction to the silicone band of the Apple Watch or metal casing of the SkyLabs CART-I ring.
- Inability to comply with trial procedures
- Participant decision

Participants may withdraw their consent, meaning that they wish to withdraw from the study completely. Their data will not be analysed, and another participant will be recruited.

In addition, the Investigator may discontinue a participant from the trial treatment at any time if the Investigator considers it necessary for any reason including, but not limited to:

- Ineligibility (either arising during the trial or retrospectively having been overlooked at screening)
- Significant protocol deviation
- Significant non-compliance with treatment regimen or trial requirements

The type of withdrawal and reason for withdrawal will be recorded in the CRF.

If the participant is withdrawn due to an adverse event, the Investigator will arrange for follow-up visits or telephone calls until the adverse event has resolved or stabilised.

## 8.12 Definition of end of study

The end of the study will be 3 months following the date of the last 12-lead ECG and 1-lead ECG. During this period, the investigators will finish adjudication and data analysis.

## 9 SAFETY REPORTING

### 9.1 Definition of Serious Adverse Events

A serious adverse event is any untoward medical occurrence that:

- results in death
- is life-threatening
- requires inpatient hospitalisation or prolongation of existing hospitalisation
- results in persistent or significant disability/incapacity
- consists of a congenital anomaly or birth defect.

Other 'important medical events' may also be considered a serious adverse event when, based upon appropriate medical judgement, the event may jeopardise the participant and may require medical or surgical intervention to prevent one of the outcomes listed above.

NOTE: The term "life-threatening" in the definition of "serious" refers to an event in which the participant was at risk of death at the time of the event; it does not refer to an event which hypothetically might have caused death if it were more severe.

### 9.2 Reporting Procedures for Serious Adverse Events

A serious adverse event (SAE) occurring to a participant should be reported to the REC that gave a favourable opinion of the study where in the opinion of the Chief Investigator the event was 'related' (resulted from administration of any of the research procedures) and 'unexpected' in relation to those procedures. Reports of related and unexpected SAEs should be submitted within 15 working days of the Chief Investigator becoming aware of the event, using the HRA report of serious adverse event form.

## 10 STATISTICS AND ANALYSIS

Descriptive statistics are reported as count and percentage for categorical variables and mean and standard deviation for continuous variables.

Adjudication of all anonymised ECGs (12-lead ECGs, 1-lead ECGs from Apple Watch and SkyLabs CART-I ring) will be performed by two Cardiologists blinded to participants' data. Any disagreements will be decided by a third Cardiologist (CI of the study). Following adjudication, the sensitivity, specificity, positive negative predictive values will be calculated for different cardiac rhythm disorders. The level agreement between adjudicators will be calculated using the Cohen's kappa.

ECG waveform analysis and intervals (PR, QRS, QT and RR) will be measured by using callipers to the nearest 0.25 mm. The first three consecutive waveforms will be analysed in each ECG and the intervals averaged. In the 12-lead ECG, it will be to the physician's discretion which lead is chosen to measure the

intervals. To investigate the level of agreement, correlation coefficient and Band-Altman plots will be generated.

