Mobile Health Technology: In the last decade, there has been an exponential growth in mobile health technologies (mHealth) with more than 400 brands and models of wearable activity monitors, including smartwatches, smartbands, rings and vests. Initially designed to track activity and heart rate, many devices now notify users of bradycardia, tachycardia and AF episodes. Most devices use very sensitive optical sensors and photoplethysmography (PPG) to analyse changes in skin colour, light intensity, and absorption to measure heart rate. In addition, advanced proprietary algorithms assess heart rate variability to diagnose AF. PPG technology has several inherent limitations that increase the number of false positive detections of AF, such as noise and artefact from changes in pressure, motion, skin tone and ambient light. More recently, an ECG sensor unit incorporated into smartwatches and rings generates a standard lead I (left arm to right arm vector) ECG which is transmitted to a smartphone app and can be exported in PDF format for further review by physicians. Wearable devices able to record 1-lead ECG can potentially identify other arrhythmias in addition to AF.

The European Society of Cardiology (ESC) recognises the pitfalls of wearable technologies in their recent guidance and recommends caution when interpreting published accuracy data from wearable devices. The guidelines state that AF diagnosis should not be based on PPG signals but can be diagnosed by physician interpretation of a single-lead ECG from a mobile or wearable device. Lastly, it highlights the need for robust validation studies prior to adopting wearable technology and 1-lead ECGs in routine clinical practice.

Undoubtedly, mHealth technology has many potential applications in healthcare, from monitoring cardiovascular risk factors and improving engagement and compliance to screening and monitoring of cardiac arrhythmias. However, the ubiquitous use of mHealth technologies— many without rigorous validation studies — will generate vast amounts of biometric data of uncertain quality and significance and will have several implications for both patients and physicians and for health economics. For patients, an ‘abnormal’ hearth rhythm detection may create significant anxiety and prompt them to take

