## 6. OBJECTIVES AND OUTCOME MEASURES

Objectives	Outcome Measures	Timepoint(s) of evaluation of this outcome measure (if applicable)
Primary Objective  Compare the accuracy of physician rhythm interpretation of 1-lead ECG generated by SkyLabs CART-I ring and Apple Watch versus 12-lead ECG (gold-standard)	Sensitivity, specificity, positive and negative predictive value of the SkyLabs CART-I ring and Apple Watch 1-lead ECGs interpretation for different cardiac arrhythmias compared with a 12-lead ECG (gold-standard)	At the time of ECG acquisition
Secondary Objective  1. Compare the accuracy of automatic AF detection of the SkyLabs CART-I Ring and Apple Watch versus a cardiologist interpretation of a 12-lead ECG (gold-standard)  2. Compare the accuracy of ECG interval measurement for the SkyLabs CART-I Ring and Apple Watch to a 12-lead ECG (gold-standard)  3. Compare the accuracy of heart rate detection of the SkyLabs CART-I ring and Apple Watch 1-lead ECG to a 30-second 12-lead ECG  4. Compare the accuracy of rhythm interpretation of SkyLabs CART-I ring 1-lead ECG to combined (plethosmography) PPG signal and 1-lead ECG.	1. Sensitivity, specificity, positive and negative predictive value of the AF detection algorithm of the Skylab CART-I ring and Apple Watch compared to a 12-lead ECG (gold-standard)  2. Level of agreement of measured interval duration between the SkyLabs CART-I ring, Apple Watch 1-lead ECG and a 12-lead ECG.  3. Correlation coefficient between the mean heart rate from simultaneous single lead and 12 lead ECG acquisitions  4. Compare sensitivity, specificity, positive and negative predictive value of the Skylab CART-I ring if a PPG signal is added	At the time of ECG acquisition

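### Accuracy of the 1-lead strips is calculated only after adjudication, so the plan reports a specialist panel's accuracy and gives none for an individual reader

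*Combined protocol and SAP*

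**What the plan says.** The primary objective in section 6 is worded: "Compare the accuracy of physician rhythm interpretation of 1-lead ECG generated by SkyLabs CART-I ring and Apple Watch", set against the 12-lead ECG. Its outcome measures are sensitivity, specificity and the two predictive values for a range of arrhythmias.

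Section 10 describes one reading process for every tracing: "Adjudication of all anonymised ECGs (12-lead ECGs, 1-lead ECGs from Apple Watch and SkyLabs CART-I ring) will be performed by two Cardiologists". These readers do not see patient information. A third cardiologist, the chief investigator, decides disagreements. Section 7 describes the same arrangement. The accuracy calculation comes next: "Following adjudication, the sensitivity, specificity, positive negative predictive values will be calculated for different cardiac rhythm disorders".

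The only statistic at reader level is this: "The level agreement between adjudicators will be calculated using the Cohen's kappa". Neither section 6 nor section 10 plans a sensitivity or specificity for an individual reader.

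On use, the background (section 5) reports guidance that AF "can be diagnosed by physician interpretation of a single-lead ECG from a mobile or wearable device". The lay summary (section 2) has the strip going to the wearer's doctor. Neither describes a panel.

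**The concern.** Adjudication is ordinary good practice for a reference standard, where the aim is to come as close to the truth as possible. The index test is different. Its accuracy includes the mistakes readers make with it, and a tie-break removes some of those mistakes before they are counted.

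Three things are at stake.

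- **What the primary figures mean.** They describe two specialists plus a decider. The setting in sections 2 and 5 is a physician looking at an exported strip.
- **False alarms.** Section 2 justifies the study by the anxiety and needless testing that a wrong abnormal finding can cause. A panel reading filters out some of those wrong findings.
- **Recoverability.** Kappa shows how often the readers differ, not how often either is right. Nothing in the planned output lets a reader of the results work back to individual accuracy.

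**Working it through.** **1. Inputs.** The reading process and the point at which accuracy is calculated come from sections 7 and 10. The plan gives no expected sensitivity or specificity, no prevalence and no between-reader correlation, and it states the sample size of 500 without a derivation. There is no planned figure to reproduce. Single-reader accuracy *s*, correlation ρ and prevalence below are assumptions. The 12-lead reference is taken as correct.

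**2. Formulas.** For a present/absent call, two readers plus a deciding third amount to a majority of three.

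- Independent errors, equal readers: P = s² + 2s(1−s)s = 3s² − 2s³.
- Errors correlated within a strip (beta-binomial, intraclass correlation ρ): P = 3E[p²] − 2E[p³], where E[p²] = s[s(1−ρ) + ρ] and E[p³] = E[p²] × [s(1−ρ) + 2ρ]/(1+ρ).

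**3. Worked case, s = 0.85.**

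- Independent: 3(0.7225) − 2(0.614125) = 0.939.
- ρ = 0.4: E[p²] = 0.85 × 0.91 = 0.7735; E[p³] = 0.7735 × 1.31/1.4 = 0.7238; P = 2.3205 − 1.4476 = 0.873.

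**4. Range.**

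| Assumed single-reader accuracy | Adjudicated, independent errors | Gain (points) | Adjudicated, ρ = 0.4 | Gain (points) |
|---|---|---|---|---|
| 0.85 | 0.939 | 8.9 | 0.873 | 2.3 |
| 0.90 | 0.972 | 7.2 | 0.919 | 1.9 |
| 0.95 | 0.993 | 4.3 | 0.961 | 1.1 |

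At s = 0.85 the gain falls to 0.5 points at ρ = 0.7 and to 0 at ρ = 1.

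**5. Direction.** With independent errors, P − s = s(1−s)(2s−1). This is positive above s = 0.50 and negative below it. At s = 0.40, P = 3(0.16) − 2(0.064) = 0.352, a loss of 4.8 points. For a rhythm that lead I shows poorly, adjudication could therefore lower sensitivity.

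**6. Predictive values.** Assume 20% prevalence and single-reader sensitivity 0.85 and specificity 0.90.

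- Single reader: PPV = 0.17/(0.17 + 0.08) = 0.68.
- Adjudicated, independent errors: 0.1878/(0.1878 + 0.0224) = 0.89.
- Adjudicated, ρ = 0.4: 0.1746/(0.1746 + 0.0648) = 0.73.

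**7. Device contrast.** A single-reader gap of 5 points between devices (0.85 against 0.90) becomes 97.2 − 93.9 = 3.3 points with independent errors, or 91.9 − 87.3 = 4.6 points at ρ = 0.4.

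**8. The one related figure in the documents.** Section 5 cites 96% sensitivity and 100% specificity for AF from watch strips in a 50-patient study, without saying how many readers were used. If that were a single-reader value, sensitivity would become 3(0.9216) − 2(0.884736) = 0.995 with independent errors (+3.5 points) or 0.969 at ρ = 0.4 (+0.9). Specificity could not rise.

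**The case against.** The strongest reply is that the target of a single physician is inferred. No section says that one physician reads the strip. The lay summary speaks of heart rhythm specialists in the plural, and much of the rationale is about validating devices. For that aim, an adjudicated specialist reading of the signal is a defensible quantity. This stands: what the documents establish is an undefined reading unit. It does not remove the point, because no section says that a panel is intended either, and a panel figure would not carry over to the use described in sections 2 and 5.

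Several stronger inferences are tempting, and the documents do not support them.

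- *Adjudication removes precisely the reader errors the study sets out to measure.* It removes only errors the readers do not share. If lead I lacks the needed information, all three may err together and the error remains.
- *The result is a best-of-three reading, or one reached by agreement.* The third cardiologist decides, and no consensus discussion is described. With more than two rhythm labels, the majority formula only approximates this process.
- *The primary estimate is biased upward, full stop.* This depends on accuracy above 50% and on errors not being fully shared. The plan covers several arrhythmias, and some may fail the first condition.

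It is also fair to say that kappa makes reader disagreement visible and that both devices receive the same adjudication. Neither supplies an individual reader's accuracy.

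**Conclusion.** The point holds in a conditional form. The text is clear that the index-test strips are adjudicated before accuracy is calculated and that no per-reader accuracy is planned. Confidence in that part is high.

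The size is uncertain. For assumed single-reader accuracy of 85% to 95%, the overstatement is about 4 to 9 points with independent errors and about 1 to 2 points at a correlation of 0.4, and it vanishes as errors become fully shared. These figures assume a binary call, equally accurate readers and a correct reference. A more accurate decider would widen the gap: with independent errors, s = 0.85 and a decider at 0.95 give 0.7225 + 2(0.85)(0.15)(0.95) = 0.965.

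A reader might go further and conclude that per-reader accuracy must replace the adjudicated result as the sole primary outcome. That is a reasonable preference, but the documents do not require it. They do call for both figures to be shown and for the adjudicated one to be named for what it is.

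**What to change.** Amend section 10 as follows.

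1. Keep two-reader adjudication with a deciding third for the 12-lead reference.
2. State that the two cardiologists read each 1-lead strip independently, and that both initial reads are recorded and retained.
3. For each device and rhythm, calculate each reader's pre-adjudication sensitivity, specificity, PPV and NPV against the adjudicated 12-lead result. Report both readers and their average, with 95% confidence intervals from a bootstrap that resamples participants, and say that the intervals are conditional on these two readers.
4. Present these beside the adjudicated 1-lead result, labelled as a panel reading.
5. State in section 6 which reading unit the primary objective refers to.

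No new recordings or readings are needed, because a meaningful kappa already requires two separate initial reads. The cost is a little more analysis and possibly lower headline figures.

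Two limits remain. Two specialists at one centre do not represent physicians in general, and a participant-level bootstrap carries no between-reader uncertainty. The same two cardiologists also read the 12-lead tracings, so their individual 1-lead calls are judged against a reference they helped to set. The report should state both.
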